#### Continuous Efficacy Measures

For the continuous efficacy measures, the change from baseline to each post-baseline period will be estimated for each treatment from repeated measures analyses as described for analysis for primary outcome, using PROC MIXED.

For the continuous secondary efficacy measures where the objective is to assess overall mean change during 6-month treatment phase, the endpoint for comparing LY2951742 with placebo will be estimated as the main effect of treatment from the MMRM analysis across Months 1-6.

#### Binary Efficacy Measures

For the repeated binary efficacy measures such as responder indicators based on the number of migraine headache days, the visitwise binary responder indicators will be analyzed using a categorical, pseudo-likelihood-based repeated measures analysis. This analysis will be implemented using the GLIMMIX procedure in SAS to compare treatments and include the

fixed, categorical effects of treatment, month, and treatment-by-month interaction, as well as the continuous, fixed covariate of baseline value.

An unstructured covariance structure will be used to model the within-patient errors (denoted by TYPE=CHOL in the RANDOM statement). RESIDUAL option in RANDOM statement will be used to specify marginal model random effect. The Newton-Raphson method with ridging will be used for nonlinear optimization (denoted by including NLOPTONS TECH=NRRIDG). The Kenward-Roger approximation will be used to estimate denominator degrees of freedom. If the model does not converge, the Fisher scoring algorithm will be utilized by the SCORING option in SAS (same as the MMRM models).

If the model still fails to converge, the model will be fit using covariance matrices in the following order (same as the MMRM models) specified by a decreasing number of covariance parameters until convergence is met:

- Heterogeneous Toeplitz = toeph
- Heterogeneous First-order autoregressive = arh(1)
- Toeplitz = toep
- First-order autoregressive = ar(1)

If necessary, both fitting algorithms will be used in the pre-specified order before proceeding to the next covariance structure in the sequence.

For models where the unstructured covariance matrix is not utilized, the sandwich estimator (Diggle et al. 1994) will be used to estimate the standard errors of the fixed effects parameters. The sandwich estimator is utilized by the EMPIRICAL option in SAS. When the sandwich estimator is utilized, the Kenward-Roger approximation for denominator degrees of freedom cannot be used. Instead, the denominator degrees of freedom will be partitioned into between-subject and within-subject portions by the DDFM=BETWITHIN option in SAS.

For the repeated binary secondary efficacy measures where the objective is to assess the proportion of patients with X% response during the 6-month double-blind treatment phase, the endpoint for comparing LY2951742 with placebo will be estimated as the main effect of treatment from the categorical MMRM analysis across Months 1-6.

For visitwise indicators of 50% responders, the results of the statistical tests at each month in the double-blinded treatment phase from categorical MMRM analysis (PROC GLIMMIX) will be used to assess the onset of 50% sustained response for LY2951742 compared to Placebo. In particular, if the key secondary measure of 50% response rate is statistically significant, then the earliest month where the statistical significance is observed and maintained for all the subsequent months during double-blinded treatment phase will be considered as the onset of 50% sustained response.

For non-repeated binary measures, such as 50% response sustained for three consecutive months until patient's endpoint in 6-month treatment phase and 50% response sustained from month 1 to

month 6, a logistic regression analysis with covariates of treatment and baseline will be conducted.

#### **Measures Conditional on the Post-baseline Number of Migraine Headache Days >0**

Some measures are conditional on the number of migraine headache days >0 such as:

- Mean severity of remaining migraine on migraine headache days
- Proportion of migraine headache days with abortive (acute) medication use
- Average number of classes of abortive medications used per migraine headache day

They will be modelled individually using the MMRM model, assuming data are missing during months without migraine headache.

#### **Analyses for Number of Weekly Migraine Headache Days in Month 1**

The number of weekly migraine headache days in Month 1 can be considered as ordinal data with possible values of 0, 1, 2, 3, 4, etc. (Note: week 4 may have more than 7 migraine headache days because of the definition. If duration of Visit 3 to Visit 5 is 31 days, then duration of week 4 is 10 days with day 22, day 23, ..., day31) It will be analyzed using an ordinal repeated measures model implemented using the GLIMMIX procedure in SAS. In this model, a proportional odds model with cumulative logit link will be used, and a random intercept will be applied to the observations for each patient to account for repeated measures. The model will include the fixed, categorical effects of treatment, week, and treatment-by-week interaction, as well as the continuous, fixed covariate of baseline number of migraine headache days (/month) and baseline number of migraine headache days by week interaction. Log (number of compliant calendar days within each week/7) will be used as the offset in the model.

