Example 4: A patient has 70 days between Visit 13 and Visit 14 (outside of visit allowance). He discontinues the study on Visit 14 (i.e., disposition is not marked as completed). Then all data will be captured and he has

- 1st half month = ePRO diary data from day 1 to day 30
- 2nd half month = ePRO diary data from day 31 to day 70.

Example 5: A patient has 35 days between Visit 13 and Visit 14. He discontinues the study on Visit 14 (i.e., disposition is not marked as completed). Then he has

- 1st half month = ePRO diary data from day 1 to day 30
- 2nd half month = ePRO diary data from day 31 to day 35.

Example 6: A patient has 14 days between Visit 13 and Visit 14. He discontinues the study on Visit 14 (i.e., disposition is not marked as completed). Then he has

- 1st half month = ePRO diary data from day 1 to day 14
- 2nd half month = No ePRO diary data

Example 7: A patient has 14 days between Visit 5 and Visit 6. He discontinues the study on Visit 6. Then he has

- Month 2= ePRO diary data from day 1 to day 14

Additionally, if the compliance rate for each monthly interval is  $\leq 50\%$ , then all endpoints to be derived from the ePRO diary data for that one-month period will be considered missing. For the post-treatment phase, the derived one-month periods (resulting from splitting two-month visit interval) will be treated similarly. For a patient who discontinued early in the double-blind treatment phase or post-treatment phase, the compliance rate for the last month of that study period will be calculated with the denominator of the maximum of 30 and the total number of calendar days in that month, i.e.,  $\max(30, \text{the total number of calendar days in that month})$ . For the rest of months and the period, the compliance rate will be calculated as described in Section 5.5.7.

In the Example 7 above, diary compliance rate for Month 2 is less than 50% even if he has no missing diary for 14 days between Visit 5 and Visit 6. Note that he discontinues and the denominator is  $\max(30, 14) = 30$ . Hence, diary compliance rate =  $14/30 * 100 < 50\%$ . Hence Month 2 diary data is considered as missing.

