**Other Efficacy Measures based on migraine headache and migraine acute treatment (not specified in Key/Other Secondary and Exploratory Efficacy Measures)**

- **Number of non-migraine headache days with aura** is calculated as the total number of non-migraine headache days with an answer of “yes” to Question 12 in a 30-day period.
- **Proportion of aura among migraine attacks** is calculated as follows: 1) among all the migraine attacks, only if aura happened on the first day of migraine attack, it will be counted as migraine attack with aura; 2) then within each period, the proportion of aura among migraine attack is calculated as the total number of migraine attacks with aura divided by the total number of migraine attacks. If the denominator is zero, then the proportion is set to missing.

Note: Some analysis listed below are based on combination medications. Combination medications (such as aspirin/acetaminophen/caffeine) will be counted in each medication category that applies (such as NSAIDs/aspirin and acetaminophen/paracetamol).

- **Number of days with abortive medication use** is calculated as the number of calendar days in a 30-day period on which an abortive medication is used.
- **Number of classes of abortive medications** is calculated as the total number of classes of abortive medications during a 30-day period.
- **Number of classes of abortive medications used on migraine headache days** is calculated as the total number of classes of abortive medications taken on migraine headache days during a 30-day period.
- **Average number of classes of abortive medication use per day** is calculated as follows for each monthly period:

$$\frac{\sum_{i=1}^5 i * n_i}{\sum_{i=0}^5 n_i}$$

Where  $n_i$  denotes the number of days during a monthly period with  $i$  class(es) of abortive medication use, and  $i = 0, 1, \dots, 5$ . Note that  $\sum_{i=0}^5 n_i = \#$  of non-missing (and complete) diary days for the period.

- **Average number of classes of abortive medications used per migraine headache day** is calculated as follows for each period:

$$\frac{\sum_{i=1}^5 i * m_i}{\sum_{i=0}^5 m_i}$$

Where  $m_i$  denotes the number of migraine headache days during a period with  $i$  class(es) of abortive medication use, and  $i = 0, 1, \dots, 5$ . If the denominator is zero (i.e., no MHD in the period), then the average is set to missing.

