- **Number of migraine headache days with menstrual period** is calculated as the total number of migraine headache days with an answer of “yes” to Question 9 in a 30-day period. (Note: The analysis population is based on female who have at least one “Question 9 =Yes” through the entire study in CGAN.
- **Number of days with abortive medication use on non-headache days** is calculated as the number of calendar days in a 30-day period on which an abortive medication is used and “Question 1 = No”.

The following analysis is based on weekly data:

- **Number of weekly migraine headache days in Month 1** is calculated as the number of migraine headache days in a 7-day period on which a migraine headache occurs. At Month 1, the first 7 calendar days will be counted as week 1, the second 7 calendar days will be counted as week 2, the third 7 calendar days will be counted as week 3, the rest of the calendar days (up to Visit 5 – 1 day) will be counted as week 4. If diary is missing on a certain day, then it is counted as non MHD day. If patients discontinues early, then the rest of the days are considered non MHD day.

**Example:** Suppose duration of Visit 3 (2018/Jan/1) and Visit 5 (2018/Jan/31) is 30 days. Then duration of week 4 is 9 days with Jan/22, Jan/23, ..., Jan/30. Note that Jan/31 is counted for Month 2.

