### Normality Assumption

To assess the robustness of the MMRM results to deviations from normality assumption, a sensitivity analysis for the raw number of migraine headache days (the total number of migraine headache days for each interval without normalization to 30-day period) will be conducted with a repeated measures negative binomial regression analysis fitted with SAS PROC GLIMMIX. The model will include treatment, month, and treatment-by-month interaction, as well as the continuous fixed covariates of baseline number of monthly migraine headache days and baseline-by-month interaction, log (number of compliant calendar days within each month/30) as the offset in the model. In case of non-convergence, baseline-by-month interaction may be excluded from the model.

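### Weekly migraine headache days in Month 1: the log-exposure offset does not suit a cumulative-logit model, and weeks with no diary days are scored zero although their offset would be log(0)

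*SAP*

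**What the plan says.** SAP 5.4.1 divides Month 1 into three 7-day weeks and a fourth week holding the remaining days up to the day before Visit 5. Its scoring rules are: "If diary is missing on a certain day, then it is counted as non MHD day" and "If patients discontinues early, then the rest of the days are considered non MHD day". No exception is made for a week without any diary entry.

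SAP 5.5.10.3 analyses the weekly counts as ordinal data: "a proportional odds model with cumulative logit link will be used, and a random intercept will be applied to the observations for each patient". Fixed effects are treatment, week, their interaction, baseline MHD and baseline-by-week. On exposure it adds: "Log (number of compliant calendar days within each week/7) will be used as the offset in the model". Compliant days are not defined for a week, and the direction of the cumulative logit is not given.

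Two other rules bear on this:

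- For months with diary compliance of 50% or less, SAP 5.4.1 says that "all endpoints to be derived from the ePRO diary data for that one-month period will be considered missing". For a patient who discontinues, the denominator for the last month is at least 30 days.
- The negative binomial sensitivity analysis of the primary endpoint (SAP 5.5.10.2, Normality Assumption) uses the same form of offset: "log (number of compliant calendar days within each month/30) as the offset in the model".

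The weekly measure stands under a heading for measures "not specified in Key/Other Secondary and Exploratory Efficacy Measures".

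**The concern.** Scoring an unobserved day as migraine-free lowers the count, so the model has to correct for the days actually observed. The SAP leaves that to the offset. There are three problems.

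1. **Link.** With a log link, adding log(days/7) multiplies the expected count by days/7, which is right for a rate. With a cumulative logit the same term shifts every cumulative log-odds by one constant, whatever the migraine rate or cutpoint. Its sign also depends on whether P(Y≥k) or P(Y≤k) is modelled.
2. **Empty weeks.** If compliant days are diary days, a week with none is scored zero in 5.4.1 but has offset log(0), so it cannot enter the model. If they are calendar days, missing diary days receive no correction.
3. **Compliance rule.** The SAP does not say whether the 50% rule overrides the zero-scoring rule for this measure.

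At stake is a false treatment difference when diary completion or early dropout differs between arms. The arm with more missing days would look better. The result would also rest on programming choices that the SAP leaves open.

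**Working it through.** **Week lengths.** Week 4 = (days from Visit 3 to Visit 5) − 21. For 31 days this gives 10, as SAP 5.5.10.3 states; for 30 days it gives 9, as in the SAP 5.4.1 example. The protocol's visit windows (14 ± 1, then 16 ± 3 days) allow 26 to 34 days, so week 4 can run from 5 to 13 days.

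**Offset against the shift needed.** Take daily migraine probability p = MHD/30 and c diary days in a 7-day week, with independent days.

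- Shift needed at cutpoint k = logit P(Bin(c,p) ≥ k) − logit P(Bin(7,p) ≥ k)
- Shift supplied = log(c/7)

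For 8 MHD per 30 days (p = 0.267) and c = 4, at k = 1:

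- P(Bin(4,p) ≥ 1) = 1 − 0.7333⁴ = 0.711, logit 0.899
- P(Bin(7,p) ≥ 1) = 1 − 0.7333⁷ = 0.886, logit 2.050
- Needed: 0.899 − 2.050 = −1.15. Supplied: log(4/7) = −0.56.

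| MHD per 30 days | Diary days | Offset | Needed, k = 1 | Needed, k = 2 | Needed, k = 3 | Share supplied at k = 1 |
|---|---|---|---|---|---|---|
| 4 | 4 | −0.56 | −0.80 | −1.16 | −1.91 | 70% |
| 8 | 4 | −0.56 | −1.15 | −1.28 | −1.79 | 49% |
| 8 | 6 | −0.15 | −0.36 | −0.37 | −0.46 | 43% |
| 12 | 6 | −0.15 | −0.53 | −0.48 | −0.50 | 29% |

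Over 4 to 12 MHD and 4 to 6 diary days, the offset supplies 29% to 70% of the shift at the first cutpoint. If it is added to the logit of P(Y≤k), fewer observed days raise the expected severity of the week less than no offset would allow for; that is, the term pushes away from the correction needed.

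**Empty weeks that survive the 50% rule.** With a denominator of 30, stopping after 15 complete diary days gives 15/30 = 50%, so the month is dropped. Stopping after 16 to 21 days gives 53% to 70%: the month is kept and week 4 is empty. A 30-day completer who misses one whole 7-day week has 23/30 = 77% and is also kept.

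**Simulation with no true effect.** The missingness rates are assumptions, since the documents give none. Daily migraine was Bernoulli, with patient rates averaging 8 per month and varying between patients; weeks were 7, 7, 7 and 9 days. The fit was the specified random-intercept cumulative logit by maximum likelihood, with counts of 6 or more pooled and empty weeks excluded under the diary-day readings. The odds ratio is for more MHD, in the arm with more missing days against the other. With complete data it was 0.99 to 1.00.

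| Missing days | Offset on P(Y≥k) | Offset on P(Y≤k) | Calendar-day reading |
|---|---|---|---|
| 5% v 5% | 1.00 | 1.00 | 1.00 |
| 5% v 7% | 0.96 | 0.91 | 0.93 |
| 5% v 10% | 0.90 | 0.80 | 0.85 |
| Dropout only, 2.5% v 5%, 50% rule not applied | 0.99 | 0.98 | 0.96 |

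At 5% v 10%, a log-link count model gave a rate ratio of 1.00 and a binomial model an odds ratio of 1.00.

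**Error rate at trial size (225 v 113), 5% v 10%.** Bias in the log odds ratio was −0.10, −0.21 and −0.16 against an SD of about 0.20. By normal approximation, rejection = P(Z > 1.96 − |bias|/SD) + P(Z < −1.96 − |bias|/SD), or about 8%, 18–19% and 12–13% for a nominal 5% test.

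**With a true effect.** At a rate ratio of 0.75 and equal 10% missingness, the odds ratio moved from 0.45 with full data to 0.47 for either sign. The count model returned 0.75.

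**The case against.** The case for leaving this as a minor clarification has real substance.

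- **Status.** The measure is outside the objective tables and has no multiplicity control. Onset of effect is judged on monthly tests (SAP 5.5.10.1). This stands and limits the importance of the point.
- **Imbalance is assumed.** Nothing in the documents predicts 5% against 10% missing days in a blinded first month. Patients must complete at least 80% of diary entries at baseline, and SAP 5.5.7 compares compliance between arms by month. At 5% v 7% with the offset on P(Y≥k), log(0.96) = −0.04 against an SD of 0.20 implies only about 5.5% rejection. The 5% v 10% results are a stress case. Seeing an imbalance, however, does not correct the estimate.
- **Dropout cases are few.** Spreading 15% discontinuation evenly over six months gives about 451 × 0.025 × 6/30 ≈ 2 patients stopping in the critical six days. Completers who miss a whole week come on top, at an unknown rate.
- **The calendar-day reading is strained.** Compliance is built on diary days elsewhere, so the third column of results carries less weight.
- **The 50% rule may simply apply.** Its wording covers diary endpoints generally. But SAP 5.4.1 extends the compliance approach to measures that need normalisation to 30 days, and the weekly count is not one of these. The ambiguity is real.
- **The replacement was less fully tested.** The comparison models gave point estimates only, under an independence working correlation; their error rates and convergence were not examined. This stands. Stating the logit direction and an empty-week rule would settle the sign and log(0) problems, but the under-correction would remain.

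**Conclusion.** The concern holds. The offset and the link do not match: even with the favourable sign, the offset supplies under three-quarters of the first-cutpoint correction over the range examined, and less at higher cutpoints for low and middling rates. With the other sign it makes matters worse. The scoring of empty weeks conflicts with the offset under the natural diary-day reading. These findings follow from the SAP text and algebra, with independent days assumed for the shifts.

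The practical size depends on unequal diary completion. There is no null bias when completion is equal, a small one at 5% v 7% with the favourable sign, and an odds ratio of 0.90 or 0.80 at 5% v 10%. GLIMMIX pseudo-likelihood may differ slightly from the maximum-likelihood fits used here. No primary, key secondary or monthly onset conclusion is affected. The specification should be corrected because it gives a wrong answer when completion differs between arms, and because the logit direction and the handling of empty weeks are left to the programmer.

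**What to change.** In SAP 5.4.1:

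- Define compliant days as days with a non-missing diary entry.
- Replace the two zero-scoring sentences with: *Weekly MHD is the number of MHD among compliant days; a week with no compliant days, including any week after discontinuation, is missing.*
- State whether the 50% monthly compliance rule applies to this measure.

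In SAP 5.5.10.3:

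- Analyse the observed weekly MHD with a log-link repeated-measures count model of the kind already in 5.5.10.2, with week in place of month and log(compliant days/7) as offset. A binomial model of MHD out of compliant days is an alternative.
- If the ordinal model is kept, label it a sensitivity analysis and state the direction of the cumulative logit.

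The cost is SAP wording and one model specification, with no new data. The main weekly result would no longer be on the odds-ratio scale of the planned ordinal model, and convergence of the replacement should be checked before it is fixed in the plan.

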#### **Time to Event Measures**

For the following time to event measures, a Kaplan-Meier curve of the time to event and treatment group comparison using log-rank test stratified by baseline MHD frequency category (<8 vs ≥8 migraine headache days per 30-day period) will be provided.

- Time to first 50% response in double-blind treatment phase
- Time to first loss of 50% response in post-treatment phase (SP III completer only)
- Time to initiation of preventative treatment for migraine or probable migraine in post-treatment phase (SP III completer only)

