Study Period IV: Only patients who do not participate in the CGAP study will move on to Study Period IV. During this 4-month phase, sites and patients will remain blinded to patients' treatment assignments. Patients will follow all study procedures during Study Period IV, but will

not receive galcanezumab or placebo. One month after Visit 12, if clinically warranted due to a worsening of symptoms, patients may start migraine prevention medications at the discretion of the investigator. The list of allowed preventive medications is provided in the concomitant medication study tool. At Visit 14 (Month 10), patients will return to the site for their last study visit and discharge from the study.

Patients who discontinue for any reason during Study Period IV will be expected to take the measurement for ET.

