7.8. Treatment after the End of the Study

7.8.1. Study Extensions

Patients who complete this study through Visit 12 (6 months) may be eligible to participate in Study I5Q-JE-CGAP (CGAP), if enrollment criteria for Study CGAP are met. Approximately 240 patients will be rolled over to the open-label study CGAP, which has 2 arms: galcanezumab 120 mg and galcanezumab 240 mg. Patients who enroll in the CGAP study will roll over directly at the end of the CGAN double-blind treatment period (Study Period III), skipping the 4-month, follow-up period (Study Period IV).

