- PROTOCOL Section 10.3.1. Regarding multiplicity adjustment, the protocol stated, “For the primary analysis and the other continuous efficacy analyses, multiplicity adjustment (120 mg versus placebo and 240 mg versus placebo), such as Dunnett’s procedure, will be used if appropriate.” The SAP stated that the multiplicity test would be performed only for the primary analysis with step-down Dunnett’s procedure to control overall type one error in this study. Originally ANCOVA with LOCF was planned for various efficacy and health outcome measures. CGAG deleted them. Hence these were deleted except for the primary efficacy analysis in CGAN (SAP [Table CGAN. 5.5](#)).
- PROTOCOL Section 10.3.2.3. Originally abortive medication related analysis were based on information collected through ePRO only. Additional information captured

through eCRF will be utilized in order to have more accurate analysis (SAP Section 5.5.8, Section 5.5.9).

- PROTOCOL Section 10.3.2.4. Originally treatment compliance was out of scope for summary. It was add to align with CGAG (SAP Section 5.5.6).
- PROTOCOL Section 10.3.3.3. SP III and SP IV combined analysis were omitted for other secondary and exploratory efficacy. Because many patients would skip SP IV and rollover to CGAP study, efficacy analysis would be less informative (SAP Table CGAN. 5.5).
- PROTOCOL Section 10.3.4. SP III and SP IV combined analysis was added for TEAE ADA to align with CGAG (SAP Section 5.5.12.1.6). There was no safety related time-to-event analyses using SP III and SP IV combined. Hence this statement is not applicable in SAP Version 2.
- PROTOCOL Section 10.3.4.4. Categorical analysis (LOCF) for TE vital and TE weight were omitted (SAP Section 5.5.12.2). “Any time postbaseline” analysis would be sufficient.
- PROTOCOL Section 10.3.4.6. Categorical analysis (LOCF) for TE laboratory were omitted (SAP Section 5.5.12.2). “Any time postbaseline” analysis would be sufficient.
- PROTOCOL Section 10.3.6.1 MIDAS analysis (each item score) for SP III and SP IV combined were omitted (SAP Section 5.5.11.2) because many patients would skip SP IV and rollover to CGAP study.

Including the above modifications/update/deletion from the PROTOCOL, followings are major changes (e.g. change of definition, a new analysis specifically for this study) from SAP Version 1 to SAP Version 2. Minor updates (e.g. clarification of definitions, and adding listings, adding examples for clarification) were not listed in general.

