- **50% responders sustained for all six months during treatment phase in the number of migraine headache days** is defined as meeting the 50% responder criteria in the number of migraine headache days for Months 1-6 in the double-blind treatment phase. Anyone else are non-responders, including those who discontinued early and those who completed 6-month treatment phase but did not meet 50% response criteria for one or more of the 6 months.
- **Time to first 50% response (in months)** is defined as the first month when 50% response is met during the double-blind treatment phase (SP III). If a patient has not met a 50% response during SP III, they will be censored at the last month where the 50% response status is not missing.
- **Time to first loss of 50% response in the post-treatment phase (in months)** is calculated for Month 6 50% responders as the time from the end of treatment phase to the first month in Study Period IV at which these patients no longer meet the 50% response criteria. Patients who continue meeting the criteria until the end of the study will be censored.
- **Time to initiation of treatment with a migraine preventive medication (in days) in the post-treatment phase** is defined as the date of start of the migraine preventive medication (based on information collected from concomitant medication electronic case report form [eCRF]) in the post-treatment follow-up phase (SP IV) minus the last visit date of SP III. If a patient did not initiate preventive treatment during SP IV, they will be censored at the disposition date of SP IV. This analysis will be conducted only for patients who entered SP IV.
- **Number of migraine headache days with photophobia and phonophobia** is calculated as the total number of migraine headache days with an answer of "yes" to Question 7 in a 30-day period.

- **Number of migraine headache days with nausea and/or vomiting** is calculated as the total number of migraine headache days with an answer of “yes” to Question 8 in a 30-day period.
- **Number of migraine headache days with aura** is calculated as the total number of migraine headache days with an answer of “yes” to Question 12 in a 30-day period.
- **Number of migraine headache days with prodromal symptoms other than aura** is calculated as the total number of migraine headached days with an answer of “yes” to Question 13 in a 30-day period.

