#### **5.5.12.1. Categorical Safety Variables**

Unless specified otherwise, the categorical safety analyses will include both scheduled and unscheduled visits. Unless otherwise specified, categorical safety analyses will only be conducted for Study Period III and Study Period IV separately.

Comparisons between treatment groups for all categorical safety measures will be made using the Fisher's exact test for Study Period III with the safety population.

Descriptive statistics only will be presented for the treatment groups in Study Period IV with the post-treatment population.

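### The log-rank test of time to loss of 50% response compares Month 6 responders who completed treatment and did not roll over, so its p-value is neither a randomised comparison nor a test of whether the drug effect is lost

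*SAP*

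**What the plan says.** The SAP subsection on time to event measures (5.5.10.3) provides a Kaplan-Meier curve and a "treatment group comparison using log-rank test stratified by baseline MHD frequency category" for three measures. One is time to first loss of 50% response in the post-treatment phase, which it restricts to patients who completed Study Period III. Table CGAN. 5.5 repeats the log-rank test under the Study Period IV column, and SAP 5.5.1.1 gives the same stratification (<8 versus ≥8 migraine headache days).

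SAP 5.4.1 defines the risk set. The measure "is calculated for Month 6 50% responders as the time from the end of treatment phase to the first month in Study Period IV" in which response is no longer met. Patients who keep response to the end of the study are censored.

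The Protocol decides who has post-treatment data. Section 5.1 says: "Only patients who do not participate in the CGAP study will move on to Study Period IV". Section 7.8.1 says: "Approximately 240 patients will be rolled over to the open-label study CGAP"; both CGAP arms receive galcanezumab.

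The SAP is aware of the roll-over problem. Its Revision History drops combined Study Period III/IV analyses for other secondary and exploratory efficacy: "Because many patients would skip SP IV and rollover to CGAP study, efficacy analysis would be less informative". For categorical safety, SAP 5.5.12.1 says: "Descriptive statistics only will be presented for the treatment groups in Study Period IV with the post-treatment population". Neither document puts a caveat, a weighting or a descriptive-only limit on the log-rank test for loss of response.

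**The concern.** Month 6 response is an outcome that treatment changes, and roll-over is settled only after six months of treatment. Conditioning on either can break the balance that randomisation gave. A placebo patient who reaches 50% response did so without the drug. A galcanezumab patient may have needed it. The two sets of responders can therefore have a different expected course off treatment, and a two-level baseline stratum does not remove that difference.

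The null hypothesis also misses the question. The objective in SAP Table CGAN. 4.2 is to assess changes in efficacy outcomes during Study Period IV. The log-rank null is equal loss of response in selected responders. Because placebo responders have no drug effect to lose, that null means neither that the effect is kept nor that it is gone. A reader of the study report could take a non-significant result as evidence for either.

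**Working it through.** **The plan's own figures.** Completers: 451 × (1 - 0.15) = 383.35, against 383 stated. Primary power: per-arm numbers 225 × 0.85 = 191.25 and 113 × 0.85 = 96.05; noncentrality 0.36 / √(1/191.25 + 1/96.05) = 2.879; two-sided Dunnett critical value 2.226 (correlation 0.334). The chance that at least one dose separates is 89.6%, against about 88% stated. Both reproduce. The documents give no power or event count for time to loss of response.

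**Size of the risk set.** Inputs: 383 completers (Protocol 10.1, SAP 5.2), taken here as Study Period III completers; about 240 roll-overs (Protocol 7.8.1); 2:1:1 allocation.
- 383 - 240 = 143, or 143/451 = 32% of those randomised.
- Split in proportion: 71.5 / 35.75 / 35.75, about 71/36/36.
- Month 6 response rates are not in the documents. Assumed: placebo 20-40%, each dose 40-60%.
- Placebo: 71.5 × 0.20 = 14.3 to 71.5 × 0.40 = 28.6, which is 6-13% of 225.
- Each dose: 35.75 × 0.40 = 14.3 to 35.75 × 0.60 = 21.4, which is 13-19% of 113.

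**Power of one comparison** (Schoenfeld, two-sided 0.05): Φ(|ln HR| √(D p(1-p)) - 1.96), with D events and p the placebo share. Assume that 50-80% lose response.
- Smallest case: D = 28.6 × 0.5 = 14.3, p = 0.5. This gives 12% at HR 1.5 and 26% at HR 2.
- Largest case: D = 50 × 0.8 = 40, p = 28.6/50 = 0.57. This gives 25% at HR 1.5 and 58% at HR 2.

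**What the p-value responds to.** The stratified log-rank test was simulated for Month 6 responders among 72 placebo and 36 single-dose non-roll-over completers, 1,500 runs per setting. Assumed: a 40% drug effect, roll-over unrelated to arm, and high or low between-patient variation. Month 6 response came out at 23% or 17% on placebo and about 50% on drug.

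| Drug effect retained | Rejection rate, high variation | Rejection rate, low variation |
|---|---|---|
| 0% | 17% (drug almost always looks worse) | 12% (same) |
| 25% | 9% | 6% |
| 50% | 6% | 6% |
| 75% | 7% | 14% |
| 100% | 21% (drug looks better) | 37% (same) |

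The selected groups differ in off-drug prognosis: the mean multiplier on migraine headache days is 0.60 on placebo and 0.74 on drug (0.77 and 0.85 with low variation). This is why full loss makes the drug look worse. More patients would not help: with ten times the numbers and high variation, the test rejects 89% of the time against the drug when the effect is simply lost, and stays null at about 50% retained.

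**A second model as a check.** Assumed: gamma patient rates (mean 8.6, shape 6), negative-binomial monthly counts (shape 8), baseline 4-14 days, and on-treatment rate ratios 0.92 placebo and 0.58 active. Response kept through two post-treatment months is 16% on placebo. On active it is 37% with the effect kept, 22% with half kept and about 13% with none kept. The curves coincide at about 75% lost, or about 60% lost when persistent patient-level variation (log-SD 0.5) is added.

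**The case against.** The strongest reply is that the plan gives this p-value no weight. It is one of three Study Period IV measures under an other secondary objective, it is not multiplicity-adjusted, and the objective is worded as assessing change rather than comparing with placebo. The SAP keeps combined Study Period III/IV models on the ITT population (MMRM for migraine headache days, GLIMMIX for 50%, 75% and 100% response) that do not condition on Month 6 response. Nor is descriptive-only reporting universal in Study Period IV: laboratory and ECG changes are still modelled by ANCOVA. All of this stands and limits the consequence. It does not restore a randomised comparison or match the test to the objective. The retained models also have missing post-treatment data for roll-over patients.

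Second, if the drug had no effect and roll-over did not depend on arm, the groups would be comparable; simulated rejection is then 5.9%. That is correct, and the point is conditional on the drug working or roll-over differing by arm.

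Third, non-significance with so few patients mainly reflects small numbers. That is true at the planned size, but the tenfold run shows that the mismatch remains with more patients.

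Several stronger readings are tempting and not supported:
- That patients choose to stay out of CGAP, or that roll-over differs by arm. The Protocol says only that completers may be eligible if CGAP criteria are met, with a target of about 240. Non-entry could reflect eligibility, the target or choice.
- That the curves already differ at Month 6. Everyone in the set is a Month 6 responder, so each curve starts at 100%.
- That placebo responders are mostly patients in a naturally low month. This depends on the model: adding persistent patient-level variation (log-SD 0.3 to 0.5) raises placebo retention from 16% to 25-38%.
- That equal curves mean almost all benefit has gone. The crossing point moves with the assumptions.

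**Conclusion.** The point holds. As written, the plan runs a between-arm test in a set chosen by Month 6 response, completion of Study Period III and non-entry to CGAP. If the drug works or roll-over differs by arm, the groups compared are not randomised groups. Equal curves cannot be read as effect kept or effect lost: under the illustrative models they coincide when roughly half to three quarters of the drug effect has gone, and with full loss the drug arm tends to look slightly worse than placebo.

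The selection is in the text and needs no assumption. The 143 follows from the plan's own figures. The group sizes, power and simulated rates rest on assumed response rates, effect size and patient variation; their direction matters, not their exact values.

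A reader might infer that the trial's efficacy conclusion is in doubt. It is not: the primary and key secondary conclusions and the planned ITT Study Period III/IV models are unaffected. This is a change that should be made to one secondary analysis.

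**What to change.** In SAP 5.5.10.3 (time to event measures) and Table CGAN. 5.5, and for consistency in SAP 5.5.1.1, remove the treatment log-rank test for time to first loss of 50% response. Instead:
- Present Kaplan-Meier curves within each arm with 95% confidence intervals and numbers at risk.
- Label them as Month 6 responders who completed Study Period III and did not enter CGAP, and state that the arms in this set are not randomised groups.
- Tabulate baseline migraine headache days, Month 6 migraine headache days and Month 6 response by arm, for completers who rolled over and those who did not.

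The data are already collected. The cost is SAP wording, one extra table and one fewer unadjusted p-value. Time to starting preventive treatment uses the same log-rank test in non-roll-over completers. It does not condition on Month 6 response, so it is outside this point, but its output could carry the same note on roll-over.
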